The AZURE trial randomized 3360 women with Stage II/III breast cancer receiving systemic therapy to zoledronic acid or not. The dosing of zoledronic acid used in this trial was 4 mg every 3-4 weeks for 6 doses, then every 3 months x 8, followed by every 6 months x 5, to complete 5 total years of treatment. Ninety-six percent received chemotherapy, only 152 patients received endocrine therapy alone. Serious adverse events were similar in both arms, and to date 14 cases of osteonecrosis of the jaw (ONJ) have occurred, all in the zoledronic acid arm. For the primary endpoint of disease-free survival (DFS) with a median follow-up of 59 months, the study shows no significant effect of zoledronic acid. In a preplanned subset analysis, a significant effect on both recurrence and overall survival was reported in women with well-established menopause (defined as more than 5 years after menopause, n=1101). This finding is unexpected and hypothesis-generating, requiring further investigation.

The AZURE presentation is in contrast to other previously reported adjuvant bisphosphonate trials suggesting clinical benefit. The ABCSG-12 study (Gnant M et al, NEJM 2009; ASCO 2010, abstract #533) demonstrated a 32% risk reduction in DFS events with zoledronic acid (4 mg every 6 months for 3 years) in a cohort of premenopausal women treated with endocrine therapy (including ovarian suppression) without chemotherapy at 62 months median follow-up. A randomized, placebo-controlled trial of daily oral clodronate for 2 years (Powles T et al, Breast Cancer Res 2006) in 1,069 patients with stage I-III breast cancer reported a reduction in bone relapse and improved survival. It is understood that this trial will be retrospectively evaluated with respect to menopausal status in the near future. The NSABP B-34 of clodronate versus placebo for 3 years in early stage breast cancer patients has not yet reported. The SWOG Breast Committee leadership feels strongly that the combined evidence of these trials, and not just a single trial, must be considered before making a definitive conclusion regarding the benefit of adjuvant bisphosphonates in specific breast cancer patient populations.

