S0307 is a randomized clinical trial of 3 different bisphosphonates in Stage I-III breast cancer patients receiving adjuvant systemic therapy. The randomization is between a dosing schedule of zoledronic acid similar to AZURE (4 mg intravenously monthly for 6 months, then every 3 months) versus oral ibandronate (50 mg po daily) versus oral clodronate (1,600 mg po daily), all given for 3 years. S0307 was activated November 15, 2005 and completed accrual February 1, 2010. All 6,097 patients have been followed for at least a year, and no patients remain in the monthly dosing portion of the zoledronic therapy.

No unexpected safety signals have emerged on study to date. Among 5,498 patients assessed for toxicity, 17 patients experienced Grade 4 toxicities, and an additional 7% have experienced Grade 3 events, primarily musculoskeletal pain. There have been 20 reported cases of ONJ, or about one case per 500 patients followed for a year.

Some important differences exist between the AZURE trial design and enrollment and **\$0307. \$0307.** delivers zoledronic acid in a similar "intensive" regimen, although it additionally evaluates two other oral bisphosphonates in the protocol. The duration of therapy in **S0307** is 3 years, compared to 5 years in AZURE. The percentage of patients who did not receive chemotherapy is much higher in \$0307 (20% versus about 4% in AZURE), which may impact benefit of bisphosphonates. S0307 mandates an end of study bone scan to provide a single time point at which bone metastases can be evaluated, with the thought that these high dose bisphosphonates might mask pain and other symptoms of bone involvement. S0307 has additional substudies evaluating fracture rates on high dose bisphosphonates, the impact of statin therapy on recurrence, and important biological correlates (using baseline tissue, serum and DNA) including predictors of bone metastases and toxicities from these drugs. We are looking carefully at the incidence and risk factors for ONJ in this study. The first interim analysis of S0307 is likely to occur in 2012 and then will occur annually thereafter. The analysis of \$0307 will include analyses in subsets defined by age, menopausal status, tumor stage, and other characteristics measured at baseline to determine if treatment effects are consistent over these factors.

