- 11.3 The primary outcome is disease-free survival (see Section 10.3). The complete Statistical Analysis Plan may be found in Appendix 19.4 as a separate document. Only a summary is provided here. The primary analysis is a log-rank survival comparison of the three groups followed by three pairwise comparisons if the overall omnibus test is statistically significant at the designated level. The analysis will be stratified by time period of randomization (3 Arms versus 2 Arms) as described in the S0307 Statistical Analysis Plan (see Appendix 19.4). Each pairwise comparison is performed at the same α level as the overall comparison. Given that the overall comparison is significant, this preserves the experiment-wise error rate at the designated level. (64) Since three active treatments are being compared, we assume that clodronate is the "standard" treatment that the newer agents are being compared against. Clodronate and placebo are being directly compared in NSABP trial B-34. A secondary analysis of overall survival (see Section 10.4) will also be performed. Stratified Cox regression will be used to estimate the hazard ratios and confidence intervals for the treatment comparisons, both unadjusted and adjusted for tumor and patient characteristics related to prognosis.
- 11.4 The sample size targets assumes a cumulative α =0.05 for the omnibus comparison of the three groups. The least effective treatment is assumed to have disease-free survival of 80% at 5 years. The least effective treatment compared to the most effective treatment is assumed to have a hazard ratio of 1.25. The third treatment is varied from 1.00 to 1.25. Power is computed by simulation assuming exponential distributions, 4.17 years of accrual, and an additional 5 years of follow-up. Power of the omnibus test depends on the distribution of the three hazard ratios with power lowest if the middle group is midway between the high and low groups (i.e. HR=1.125). Given a significant omnibus test, pairwise comparisons will be performed..

HR = 1.0, 1.25, 1.25 (zoledronic acid (Z) = ibandronate (I) > clodronate (C))

	Power	Power	Power	Power
	Omnibus	Z vs C	I vs C	Z vs I
Equal allocation (n=1500, 1500, 1500)	86%	78%	78%	NA
Equal allocation (n=1800, 1800, 1800)	91%	86%	86%	NA
Unequal allocation (n=2000, 1400, 2000)	93%	89%	84%	NA

HR = 1.0, 1.0, 1.25 (zoledronic acid > ibandronate = clodronate)

	Power	Power	Power	Power
	Omnibus	Z vs C	I vs C	Z vs I

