Menopausal status (select one): Pre (< 6 mo since LMP and no prior bilateral ovariectomy and not on estrogen replacement)
Post (prior bilateral ovariectomy OR > 12 mo since LMP with no prior hysterectomy)
Above categories not applicable AND age < 50 (pre)
Above categories not applicable AND age≥ 50 (post) Height: cm Weight: kg BSA: m²
DISEASE DESCRIPTION
Date of Initial Diagnosis of Primary Tumor: / / / /
Tumor Laterality (select one): Left Right Bilateral
Pathologic Primary Tumor Size:cm (Maximum diameter of the invasive component; if multiple lesions, use longest lesion)
Number of Positive Lymph Nodes: (If sentinel node biopsy and axillary node dissection were performed, enter the sum of positive nodes.)
Receptor Status: (≥10 is positive if measured in fmols/mg cytosol protein. Otherwise use institutional standards; borderline results should be reported as positive.)
ER Status: Negative Positive
PgR Status: Negative Positive
Was HER-2/neu status determined? No Yes
If Yes, HER-2/neu final diagnosis: Positive* Negative Equivocal * (Positive is DAKO3+, FISH+, or institutional standard.)
TREATMENT WITH STATINS
Is the patient currently taking a statin: atorvastatin (Lipitor), pravastatin (Pravachol), simvastatin (Zocor), lovastatin (Mevacor), fluvastatin (Lescol), rosuvastatin (Crestor)?
Length of time on statin:
PATIENT PREFERENCE
If oral and intravenous bisphosphonates are equally effective in preventing breast cancer recurrence in the bone, which would the patient prefer to receive? Note that the answer to this question will not in any way affect which treatment the patient is randomly assigned to on this study.
☐ Oral (taken daily)
Intravenous (by vein - given once a month for the first 6 months, and once every 3 months after)

continued on next page

20161

SOUTHWEST ONCOLOGY GROUP S0307 PRESTUDY FORM

Page 3 of 3

SWOG Patient ID	SWOG Study No. S 0 3 0 7	Registration Step 1
Patient Initials(L, F M)		

Patient Initials(L, F M)
PRIOR TREATMENT RELATED TO THIS CANCER:
PRIOR TREATMENT RELATED TO THIS CANCER
Most Extensive Primary Surgery (select one): Partial mastectomy/lumpectomy/excisional biopsy Mastectomy, NOS
Date of Most Extensive Primary Surgery: / / / (If required, use last re-excision date)
Was sentinel node sampling performed? Yes No
Sentinel Node Biopsy Date: / / /
Sentinel Node Biopsy Results: Positive Negative
Was axillary dissection performed? Yes No
Date of Axillary Dissection: / / /
SYSTEMIC TREATMENT FOR THIS CANCER

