Chemotherapy (select one): Currently receiving Planned Not planned Completed If completed, Date chemotherapy ended: Currently receiving: Currently receiving: SERM (e.g., tamoxifen, raloxifene) Planned Aromatase inhibitor (e.g., anastrazole, letrozole, exemustane) Not planned Ovarian suppression

SOUTHWEST ONCOLOGY GROUP S0307 TREATMENT SUMMARY FORM

Page 1 of 1

SWOG Patient ID SWOG Study No. S 0 3 0 7 Registration Step 1
Patient Initials(L, F M) Reporting Period: 0-6 months 0 6 mo-1 yr 1 yr-2 yr 2 yr-3 yr
Institution/Affiliate Physician
Participating Group: Group Name/Study No./Patient ID/// Instructions: Please complete this form at 6 months, 1 year, 2 years, and 3 years. All dates are MONTH, DAY, YEAR. Explain any blank dates or fields in the Comments section. Place an X in appropriate boxes. Circle AMENDED items in red and write AMENDE across the top of the form.
DISEASE STATUS
Date of Last Clinical Assessment: / / (submit Follow Up form if patient has relapsed)
Date of Last Contact or Death: / / /
Vital Status: Alive Dead (submit Notice of Death form)
TREATMENT STATUS Assigned Treatment Arm: Arm 1 Arm 2 Arm 3
Was the patient treated on the assigned arm during this reporting period? Yes No, specify reason in comments
Treatment Begin Date (for this reporting period): / / / /
Treatment End Date (for this reporting period): / / / / / / / / / / / / / / / / / / /
Were there any dose modifications or additions/omissions to protocol treatment (during this reporting period) No Yes, planned (per protocol guidelines), specify in comments Yes, unplanned (not per protocol guidelines), specify in comments For Arms 2 and 3: In the past month, how many pills did the patient miss?
Did the patient receive any chemotherapy during this reporting period? Yes No
Did the patient receive radiation therapy during this reporting period? Yes No
Did the patient receive any hormone therapy during this reporting period? Yes No If yes, SERM (e.g., tamoxifen, raloxifene) Aromatase inhibitor (e.g., anastrazole, letrozole, exemestane) Ovarian suppression Is the patient currently taking a statin: atorvastatin (Lipitor), pravastatin (Pravachol), simvastatin (Zocor),
Iovastatin (Mevacor), fluvastatin (Lescol), rosuvastatin (Crestor)?
Has the patient experienced a bone fracture since submission of the last treatment summary form? Yes No If yes, indicate site: Hip Spine Pelvis Wrist Arm Leg Ankle Was the fracture traumatic (from greater than standing height)? Yes No

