In the absence of temporal drift, stratification is not strictly necessary, but accounting for it causes little loss in power. If there is temporal drift, then failure to account for it could lead to bias when changing allocation probabilities. Simulation for extreme drift in DFS over time shows that alpha is inflated to 7% under the null hypothesis when stratification is not used. Even if the third group is "metered" (randomization for ibandronate continues at a low level), there is still inflation of alpha in the presence of temporal drift. This is due to imbalance in projected outcomes since patients have different projections over time. Thus, any change in randomization allocation must be addressed in the analysis. Our simulation shows that alpha is correctly maintained by stratification in the presence of temporal drift.

With regard to power, maximal power is obtained using stratified model (1) above for the omnibus test. Power is 85% to 92% depending on the distribution of the three groups. Pairwise comparisons range in power from 83% to 90% for the two extreme groups. These estimates are based on an expected final sample size of 5,600.

Therefore, the primary analysis will be based on Model (1) to obtain the significance of the overall comparison and the pairwise comparison of zoledronic acid to clodronate. The two remaining pairwise comparisons (ibandronate vs. clodronate and ibandronate vs. zoledronic acid) are based on the first time period only when there was randomization to ibandronate.

Secondary comparisons will include adjustment for prognostic factors such as HER2 status, AJCC stage, and hormone-receptor status. Subgroup analysis will include determination of the hazard ratios (compared to clodronate) separately by age group, race, Her2 status, hormone-receptor status, AJCC stage, and type of adjuvant treatment received. These will be presented in a forest plot so that apparent discrepancies from the overall results will be visually apparent. These latter analyses are exploratory as there are no expected interactions of treatment with these prognostic factors.

Reference

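### Minor, exploratory only: the SAP's subgroup plan gives no estimate of how subgroups differ, sets no time point for the adjuvant-treatment subgroup, and does not list menopausal status

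*Combined protocol and SAP*

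**What the plan says.** The last substantive paragraph of Appendix 19.4 (Analysis) plans hazard ratios relative to clodronate "separately by age group, race, Her2 status, hormone-receptor status, AJCC stage, and type of adjuvant treatment received". On display it says: "These will be presented in a forest plot so that apparent discrepancies from the overall results will be visually apparent". On status: "These latter analyses are exploratory as there are no expected interactions of treatment with these prognostic factors". No interaction term, ratio of hazard ratios or heterogeneity test is specified for these six factors.

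Protocol section 11.3 adds, for the trial as a whole: "Stratified Cox regression will be used to estimate the hazard ratios and confidence intervals for the treatment comparisons".

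The letter to investigators on the AZURE result, in the front matter, is later than the SAP: it reports accrual as complete, while the SAP still treats closure as a future event. It says the analysis will include subsets by age, "menopausal status, tumor stage, and other characteristics measured at baseline to determine if treatment effects are consistent over these factors". It gives no method.

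The Prestudy Form (section 18.0) collects both variables at issue: "Menopausal status (select one): Pre (< 6 mo since LMP and no prior bilateral ovariectomy and not on estrogen replacement", with further categories, and "Chemotherapy (select one): Currently receiving Planned Not planned Completed". The Treatment Summary Form asks about chemotherapy and hormone therapy again in each reporting period. Section 5.3 allows enrolment before systemic therapy begins.

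**The concern.** There are three gaps in one paragraph.

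1. **No measure of difference.** The stated purpose is to see whether effects are consistent. A separate hazard ratio for each subgroup, even with a confidence interval, describes that subgroup alone and does not measure how far two subgroups differ. The documents specify interactions elsewhere: objective 1.6 (PTHrP and N-telopeptide), the statistical plan of Appendix 19.3 (SNP by treatment), and the third coefficient of Model (2) in 19.4.

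2. **Adjuvant treatment received.** A woman registered with chemotherapy planned who never receives it falls in one group by the Prestudy Form and in another by the Treatment Summary Forms. The second reading uses information from after randomisation, which the assigned drug, toxicity or early recurrence could influence. Two analysts could build different subgroups from the same text.

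3. **Menopausal status.** The letter promises this subset and the form collects the variable, but the SAP list does not name it.

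At stake is how exploratory results are read, above all the risk that chance variation in a forest plot is reported as a drug working in one group and not in another.

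**Working it through.** The subgroup paragraph contains no figure to reproduce. The check is how much two subgroup hazard ratios would differ by chance when the true effect is the same in both.

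**Inputs**
- Expected events under the null: 1,314 (section 11.5).
- Target accrual: 5,400, of whom 2,000 zoledronic acid and 2,000 clodronate (section 11.2).
- Share without chemotherapy: 20% (letter).
- Assumption: events are proportional to patients across arms and subgroups.

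**Events, zoledronic acid versus clodronate:** 1,314 × 4,000/5,400 = 973.

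**Formula.** With equal allocation, the variance of a log hazard ratio is about 4/events. For a factor that splits the E events into shares s and 1 − s, the log ratio of the two hazard ratios has

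SE = √(4/(sE) + 4/((1 − s)E)),

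and with no interaction its 95% chance range is exp(±1.96 × SE).

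| Split | Events per subgroup | SE | 95% chance range |
|---|---|---|---|
| 50/50 | 487 / 487 | 0.128 | 0.78 to 1.29 |
| 20/80 (no chemotherapy / chemotherapy) | 195 / 779 | 0.160 | 0.73 to 1.37 |
| 599/4,801 (planned non-White / White, section 2.0 table) | 108 / 865 | 0.204 | 0.67 to 1.49 |

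**Sensitivity to the event count (even split)**
- The 1,314 is approximate. Exponential survival with 80% at 5 years gives 1,458 events under uniform accrual over 4.17 years plus 5 years of follow-up, and 1,369 under an assumed back-loaded accrual. The plan's monthly accrual schedule is not given, so this is not called an error. Scaled by 4,000/5,400, these give 1,080 and 1,014 events, with ranges of 0.79 to 1.27 and 0.78 to 1.28.
- On actual accrual, (6,097 − 1,567) × 1,314/5,400 = 1,102 events, with a range of 0.79 to 1.27.
- Ibandronate versus clodronate, first randomisation period only: 1,567 + (4,747 − 1,567)/2 = 3,157 patients. At 24.33% this is 768 events, with a range of 0.75 to 1.33. The whole-trial event fraction probably understates events here, because these patients have the longest follow-up; the true range would then be somewhat narrower.

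**What an interaction analysis could detect (even split, 973 events).** For a true ratio of hazard ratios of 1.25, power at two-sided 0.05 is Φ(ln 1.25/0.128 − 1.96) = 41%. The ratio detectable with 80% power is exp(2.80 × 0.128) = 1.43.

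**Adjuvant subgroup, forms side by side.** The Prestudy Form allows currently receiving, planned, not planned or completed for chemotherapy. The Treatment Summary Form asks whether any was given in the period, at 6 months and 1, 2 and 3 years. The word received in the SAP fits either source, and the SAP names neither. The letter refers to characteristics measured at baseline but does not name adjuvant treatment among them.

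**The case against.** The case on the other side is substantial.

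- **The analyses are labelled exploratory, with a reason.** That stands and limits the point to a minor one. A reader might infer that the main inference is at risk. It is not: the omnibus test, the pairwise tests and their alpha do not depend on this paragraph.
- **The SAP sets no decision rule by eye.** This also stands. The sentence describes a display. A reader might infer that subgroups will be declared different when one interval excludes 1 and the other does not. The SAP proposes no such rule, so this point does not rest on how often that pattern occurs.
- **The SAP compares subgroups with the overall result, not with each other.** On that scale an even split at 973 events gives SE = √(4/486.7 − 4/973.3) = 0.064 and a range of 0.88 to 1.13. This is the same information on a different scale, and the plan gives no estimate on either.
- **No passage plans a post-randomisation subgroup.** Correct. The letter's reference to baseline suggests the intention, and the SAP calls these prognostic factors. What remains is that the SAP wording permits the other reading.
- **Menopausal analysis is not missing.** Correct. The letter commits to it, and the SAP list is worded as what the analysis will include, so it is not closed. This part is only alignment of two texts.
- **Interaction tests would be weak and numerous.** Correct, and a reason to lead with estimates rather than tests. It does not favour a plot with no measure of difference, which rests on the same data.

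**Conclusion.** The point holds as a minor one, confined to exploratory analyses. The SAP should say how differences between subgroups will be estimated, because the letter gives consistency as the purpose of the subsets. With about 973 events and no interaction, two subgroup hazard ratios can differ by a ratio of roughly 0.78 to 1.29 by chance for an even split, and 0.73 to 1.37 for 20/80. The adjuvant subgroup needs a time point, so that membership cannot depend on events after randomisation. Adding menopausal status only brings the SAP into line with a recorded intention.

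The figures assume 4/events for the variance, events proportional to patients, and illustrative splits (20% is the stated no-chemotherapy share). The even-split range changes little over 973 to 1,102 events.

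A reader might also infer that a menopausal subset here would confirm or refute AZURE. The documents do not support that. AZURE's subset was "women with well-established menopause (defined as more than 5 years after menopause, n=1101" and its comparison was with no zoledronic acid. The Prestudy Form uses a different definition of menopause, and every patient in this trial receives a bisphosphonate.

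**What to change.** In Appendix 19.4:

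(a) For each factor and each contrast with clodronate, report the treatment-by-factor interaction estimate (the ratio of hazard ratios) with its confidence interval, from the period-stratified Cox model. Ibandronate contrasts use the first randomisation period only, as 19.4 already does for its pairwise tests. For a factor with three or more levels, such as AJCC stage, state the reference level and give one joint heterogeneity test. Label all of these exploratory and state how many were done.

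(b) Define the adjuvant subgroup by treatment received or planned as recorded on the Prestudy Form (due within 14 days of registration, section 14.4), not by later Treatment Summary Forms. Take the hormone-therapy coding from the options on the form itself, because that field is not legible in the text available here.

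(c) Add menopausal status by the Prestudy Form definition.

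**Cost.** A few lines of SAP text. Menopausal status, adjuvant treatment and most listed factors are on the Prestudy Form; race and date of birth are on the Registration Form. Power is low, so a non-significant interaction must not be read as proof of consistency. With seven factors and two contrasts, one test each, there are 14 tests. The chance of at least one false signal at 0.05 is up to 1 − 0.95^14 = 51% if they are independent, and lower where factors overlap, as age and menopause do. The estimate and its interval should therefore lead, with the count stated beside them.
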